# Part A only:

For assessment of safety by the IDSM, with regard to dropping a dose level for futility, 3 evaluable patients, defined as compliance of ≥75% of doses for that dose level, are required. Patients will be replaced if necessary to fulfill this requirement.

# 10.6.2 Efficacy Analysis Population

All patients who have enrolled in the study will be included in the Intent to treat (ITT) population. Enrolled patient is defined as a patient who signed the informed consent form and met eligibility criteria. Efficacy analysis will be based on the ITT population.

### 10.6.3 Pharmacokinetic Analysis Population

All patients who have received at least one dose of rilzabrutinib and have at least one measurable plasma concentration value will be included in the PK analysis. The Pharmacokinetic Analysis Population will be used for all PK analyses.

# **10.7** Patient Numbers and Treatment Assignments

As they are enrolled in the study, patients will be assigned a unique consecutive number. The site, in conjunction with the Sponsor, will be responsible for assignment of all unique patient numbers and dose assignments.

# 10.8 Patient Disposition, Patient Replacement, and Demographics and Baseline Characteristics

### 10.8.1 Disposition

The numbers of patients enrolled, completing, and withdrawing, along with reasons for withdrawal, will be tabulated. The number of patients in each analysis population will be reported.

# 10.8.2 Replacement of Patients

Patients prematurely discontinued from the study, for reasons other than TEAEs, may be replaced at the discretion of the Sponsor to ensure adequate numbers of evaluable patients. Each patient who provides informed consent will be assigned a unique patient identifier (USUBJID). Patients recruited to be replacement patients will be assigned the next available patient identifier.

15 May 2024

Version number: 1

# 10.8.3 Demographics and Baseline Characteristics

Demographic and baseline characteristics (age, sex, race, ethnicity, weight, height, and body mass index) will be summarized for the Safety Analysis Population using descriptive statistics. No formal statistical analyses will be performed, and no inferential statistics reported.

Prior and concomitant medications will be listed, classified using World Health Organization Drug Dictionary (WHODD) Anatomical Therapeutic Chemical classes and preferred terms.

Baseline demographics and patient characteristics will be summarized for the Safety Population.

# 10.9 Efficacy and Exploratory Analysis

### Part A

Qualitative efficacy data will be summarized by frequencies and percentages. Quantitative efficacy data will be summarized by descriptive statistics (arithmetic mean, standard deviation, median, minimum, and maximum). Data will be summarized over time by dose level and overall. The time course of mean changes in platelet count over time will also be described graphically, annotated for dosing levels. All analyses will be based on the Intent-to-treat (ITT) Population.

Full details of the analyses for Part A will be provided in the Statistical Analysis Plan (SAP).

### Part B

Qualitative efficacy data will be summarized by frequencies and percentages. Quantitative efficacy data will be summarized by descriptive statistics (arithmetic mean, standard deviation, median, minimum, and maximum). The time course of mean changes in platelet count over time will also be described graphically. All analyses will be based on the ITT Population.

Full details of the analyses for Part B will be provided in the SAP.

# 10.10 Safety and Tolerability Analysis

The incidence, severity, and relationship of TEAEs, laboratory tests, rescue treatment usage, and vital signs will be summarized descriptively. Qualitative safety data will be summarized by frequencies and percentages at each dose level, using the time boundaries of that dosing level (Part A only). Quantitative safety data will be summarized by descriptive statistics (arithmetic mean, standard deviation, median, minimum, and maximum) at each dose level (Part A only) and overall for Part B. Summaries will also be presented for the change from baseline, when

15 May 2024 Version number: 1

appropriate. The proportion of patients with a Grade 2 or higher bleeding event will also be summarized. Non-TEAEs will be described in separate listings.

### 10.10.1 Adverse Events

The original verbatim AE terms recorded on the patient's case report form (CRF) by the Investigator will be standardized by assigning preferred terms and system organ classes from the most recent available version of the Medical Dictionary for Drug Regulatory Affairs (MedDRA).

Adverse events will be codified using the NCI CTCAE v5.0, which provides a mechanism for grading the severity of the AE.

Treatment emergent adverse events include all AEs that start on or after the first dose of study medication, or AEs that are present prior to the first dose of study medication, but worsen after the first dose of study medication up to and including the final study medication dosing date. Adverse events that occur after the first dose of study medication or worsen after the first dose of study medication are treatment-emergent adverse events (TEAEs). Adverse events that occur prior to the first dose of study medication are pre-treatment adverse events (ie, non-TEAEs). The number and percent of patients with any TEAEs will be displayed by system organ class and preferred term by dosing level and overall. Within each preferred term, patients will be counted only once if they had more than one event reported during the dosing period. The same summary will be performed for all serious TEAEs and all TEAEs causing discontinuation of study drug.

Treatment-emergent adverse events will also be summarized by greatest reported severity grade (Grades 1–5) for each event/preferred term. Counts will indicate patients reporting one or more TEAEs that map to the severity grade classification for each preferred term. At each level of summarization (system organ class or event preferred term) patients are only counted once. TEAEs will be summarized by greatest reported relationship in a similar manner. A listing will be produced for all patients who reported serious TEAEs or who discontinued study medication due to TEAEs.

All TEAEs will be listed individually by patient. In addition, a separate listing will be produced for AEs that are not treatment-emergent.

# 10.10.2 Clinical Laboratory Tests

All clinical laboratory data will be stored in the database in the units in which they were reported. Normal ranges for the local laboratory parameters must be provided to Principia/designee before the study starts. Patient listings and summary statistics at each assessment time, including change from baseline, will be presented using the International System of Units (SI units; Système International d'Unités). Laboratory data not reported in SI units will be converted to SI units before analysis.

### Part A

[figure not shown]
Clinical laboratory results will be summarized descriptively for baseline and each time point. The numerical change from baseline to each time point will be computed. Exploratory analysis

15 May 2024 Version number: 1

of the relationship between dose level and laboratory changes will be explored if any are seen in the initial analyses. In addition, laboratory shift tables will be provided for all laboratory parameters where low/normal/high or abnormal/normal status can be ascertained for shift from baseline to each time point. Listings of individual laboratory parameters by visit with normal ranges and abnormality assessments will also be completed by patient.

# Part B

Clinical laboratory results will be summarized descriptively for baseline and each monthly clinic visit. The numerical change from baseline to each visit will be computed. Laboratory shift tables will be provided for all laboratory parameters where low/normal/high or abnormal/normal status can be ascertained for shift from baseline to each monthly clinic visit. Listings of individual laboratory parameters by visit with normal ranges and abnormality assessments will also be completed by patient.

# 10.10.3 *Vital Signs*

Vital signs data will be presented by individual listings. Systolic blood pressure values <90 or >140 mmHg and diastolic blood pressure values <60 or >80 mmHg will be flagged as outside the normal range. Resting heart rate <40 or >100 beats per minute will be flagged as outside the normal range. Descriptive statistics of values and changes from baseline (mean, median, standard deviation) will be reported for quantitative variables separately for each dosing level, using the time boundaries for that level in Part A and overall in Part B. In addition, tabular and graphical summaries will be used, as appropriate.

# 10.10.4 Rescue Medication, DLTs, and Bleeding Scale Scores

The percentage of patients receiving rescue medication at each dosing level (Part A only) and at any time during dosing for Part A, and at any time during dosing for Part B.

15 May 2024

Version number: 1

The percentage of patients with a DLT will be summarized at each dosing level, overall for Part A, and overall for Part B.

Bleeding scale (IBLS) scores will be summarized over time at each dosing level, overall for Part A, and overall for Part B.

### 10.10.5 Concomitant Medications

The original terms recorded on the patients' CRF by the Investigator for concomitant medications will be standardized by assigning preferred terms from the WHODD drug terms dictionary for treatments or coded via generic name of the concomitant medication.

Concomitant medications will be presented in summary tables and listings.

# 10.11 Pharmacokinetics Analyses

# Part A

Pharmacokinetic data will be summarized using descriptive statistics, tabulated, and displayed graphically as appropriate. Non-compartmental analysis will be utilized to derive PK parameters for each individual. Pharmacokinetic data may also be pooled with the data from other studies for population PK modeling. Individual patient PK values within this study may be used for exploratory analyses of exposure and effect.

### Part B

Pharmacokinetic data will be summarized using descriptive statistics, and tabulated, and displayed graphically as appropriate. Pharmacokinetic data may also be pooled with the data from other studies for population PK modeling.

# 10.12 Statistical Analysis Plan

A detailed SAP will be developed and finalized before the study database is locked, which will supersede the statistical analysis methods described in the protocol.

# 11 SAFETY AND TOXICITY MANAGEMENT

This section provides detailed information on reporting requirements and interpretation of safety assessments for AEs and reporting requirements for SAEs. Guidance and reporting requirements for pregnancy are also outlined below.

15 May 2024

Version number: 1

# 11.1 Independent Data Safety Monitor (IDSM) and Safety Monitoring Committee (SMC)

### Part A

An IDSM who is not a study Investigator will be chosen from expert clinicians in the ITP field. A Safety Monitoring Committee (SMC), comprised of the IDSM as Chairperson, lead Investigator, Study Medical Monitor, and Sponsor's Medical Monitor, will closely supervise the conduct of the study. The IDSM will make "sentinel cohort" safety evaluations.

The "sentinel patients" for each dose level will have their data reviewed by the IDSM, in order to choose the starting dose for additional, new patients. After review, the IDSM may determine that a starting dose for new patients should be dropped for futility (lack of platelet response), increased to the next planned dosing level, kept the same, or reduced. New patients entering the study will commence at the dose level determined by the IDSM based on:

- If ≥2/3 or ≥2/6 of those sentinel patients have a DLT at any dose level, that level shall be determined the "Maximal Administered Dose" and starting doses (new patients) and continuing doses (patients already on study) set at lower dosing levels (or study suspended if the current sentinel dose cohort was 200 mg QD)
- If two or more sustained platelet responses (3 of 4 counts) in the sentinel patients are seen at the current starting dose level the starting dose will not be escalated.

The SMC will meet approximately quarterly and recommend study modification or termination to the Sponsor, based on review of safety and efficacy information. Any SMC findings that impact the safety of patients in this study will be immediately reported to the local Competent Authority (CA) and IRB/EC.

An SMC Charter outlining the SMC composition and responsibilities will be in place prior to the first scheduled meeting.

### Part B

There will be no independent SMC in Part B.

Specific assessments to evaluate treatment safety include the following: the frequency, severity and relationship of AEs, clinical laboratory test changes, physical examination, and vital signs. The assessments will be conducted as part of ongoing medical monitoring and at Sponsor Quarterly Safety Reviews where safety events and trends across rilzabrutinib studies are considered.

# 11.2 Adverse Event Collection Period

The AE Collection Period begins at the time of the first screening/eligibility assessment and ends at the end of the study for each patient.

15 May 2024

Version number: 1

### 11.3 Adverse Events

An AE is any untoward medical occurrence in a patient or clinical investigation patient administered a pharmaceutical product and which does not necessarily have to have a causal relationship with the intervention. An AE can therefore be any unfavorable and unintended sign (including an abnormal laboratory finding, for example), symptom, or disease temporally associated with the use of an investigational product, whether or not considered related to the product. All AEs encountered during the clinical study will be recorded in detail in the source documents and entered in the CRF from the date of patient consent throughout the study follow-up period. Pre-existing conditions that worsen during a study are reported as AEs, with the expectation of expected variation in ITP disease activity itself.

Unexpected progression, signs, or symptoms of the disease under study (ITP) are not AEs and are not to be recorded on the AE page of the CRF unless the event meets the definition of an SAE or is not consistent with the typical clinical course of the patient's disease as established by the patient's medical history. Worsening of the disease under study or other disease-related symptoms should be recorded as an AE only if the event meets the definition of an SAE or is not consistent with the typical clinical course of the disease.

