# 3.4 Outcome Measures of the Study: Part B

# 3.4.1 Primary Safety Endpoints

Safety will be assessed by the incidence, severity, and relationship of TEAEs, including clinically significant changes in physical examination, laboratory tests, and vital signs. Bleeding TEAEs will be tabulated and a proportion of patients with a Grade 2 or higher bleeding event will be provided.

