Synopsis, Study endpoints Part B; Section 10.3, Secondary efficacy endpoints	Text moved to Statistical Methods Part B section of synopsis.	Per analysis population definition in Section 10.7.2.
Synopsis, Planned number of patients; Section 4.7, Number of patients	Revised text to specify enrollment of "approximately 60 patients" in Part A and "approximately 23 patients" in Part B.	Clarification of expected enrollment.
Synopsis, Patient selection Part A; Section 6.1.2, Exclusion criteria	Updated exclusion text to specify "hepatitis B (surface antigen and core antibodies unrelated to vaccination)."	Updated to clarify intended exclusion for Hepatitis B surface antigen.
Synopsis, Patient Section Criteria Part B; Section 6.2.2 Exclusion criteria	Criterion 17: Revised text intent for exclusion or inclusion of patients meeting hepatitis B virus serology, and follow-up for those patients who are enrolled with stated conditions.	Clarification of intent for exclusion of patients.
Synopsis, Safety assessments and monitoring Part B	Revised text to state that "The assessments will be conducted as part of ongoing medical monitoring and at Sponsor-Quarterly Safety Reviews where safety events and trends across rilzabrutinib studies are considered." Removed text regarding independent SMC.	As the treatment-emergent adverse event profile is acceptable for continuation of the study, there will not be a Safety Monitoring Committee in Part B.  Safety in Part B will be monitored via Sponsor Quarterly Safety Reviews established after the original protocol was implemented.
		Sponsor Quarterly safety reviews will include analyses of safety events and trends across rilzabrutinib studies.
Synopsis, Statistical methods Part A	Revised text as follows: "The proportion of patients with a Grade 2 or higher bleeding events will also be summarized."	Updated to reflect decision to summarize all bleeding events.
Synopsis, Statistical methods Part B; Section 10.6, Determination of sample size Part B	Updated text to reflect revised sample size estimate.  Updated to reflect changes to the efficacy analysis and the revised sample size (deleted text), and to reflect the move of the inserted text from the Study Endpoints Part B section of the synopsis.  Updated to reflect decision to summarize all bleeding events.	Updates to reflect revised sample size estimate, efficacy analysis, and summarization of all bleeding events.

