Updated text regarding pre-existing conditions to be reported as AEs.	The platelet count is part of the assessment of efficacy in the ITP patients. As such it is expected to fluctuate and is captured in the efficacy assessments. Text updated in this section to clarify that the disease under study is only recorded as an event if it meets serious criteria or is not consistent with the typical clinical course for that patient.
Text revised.	Text streamlined for operational ease of use to locate the definition of an SAE.
Revised text specifying the 4 minimum criteria for a valid SAE report.	Streamlined text for operational ease and reconciliation with the safety database.
	Added text for Part B.  Added permitted concomitant medications for Part B.  Added "Part A" before existing text. Added text for Part B.  This section was deleted.  This section was deleted.  Added text for Part B statistical analysis.  Text revised.  Updated text to define the reported AEs that start before the first dose of study drug as pre-treatment events and those events that start after the first dose of study drug or worsen after the first dose of study drug as TEAEs.  Added text for Part B.  Text revised.  Revised text to clarify that the history of rescue medication collection in Part A was not limited to 12 weeks and that Part B will assess only 1 dose of PRN1008.  Updated text regarding pre-existing conditions to be reported as AEs.  Text revised.

Section # and Name	Description of Change	Brief Rationale
	Revised text for SUSAR reporting.	Clarified that expectedness for a SUSAR is based upon what is listed in the IB. Clarified that individual SUSARs are sent to all sites which is expected until the site is officially closed for the study.
Section 16, references.	Reference added for Kuter DJ et al, 2019.	Addition of ASH reference in support of preliminary data provided in protocol Section 2.3.
Appendix 3, Schedule of assessments (Part A)	Footnote 10 revised.	Updated for clarify and for operational ease.
Appendix 4, Schedule of assessments (Part B)	New table added.	Inclusion of Part B of the study.
Throughout document	Global changes to headings and appendix numbering as follows: Revised heading titles to identify Part and the addition of new headings for Part B.  Appendix numbers revised to accommodate the addition of the schedule of assessment for Part B (Appendix 4).	Editorial changes.

Version number: 1

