Analysis of all adverse events

The overview of TEAE with the details below will be generated:

- Any TEAE
- Any grade \geq 3 TEAE
- Any treatment emergent SAE
- Treatment emergent SAE related to IMP as per Investigator's judgment
- TEAE leading to death
- Grade 5 TEAE (any TEAE with a fatal outcome during the treatment-emergent period)
- Any TEAE leading to permanent IMP discontinuation
- TEAE related to IMP as per Investigator's judgment
- Bleeding events (Intensity Grade 2 or higher)
- Infection (Intensity Grade 2 or higher)

The AE summaries of Table 5 will be generated with number (%) of participants experiencing at least one event. TEAE will be provided for main treatment-emergent period, LTE treatment-emergent period respectively.

Table 5 - Analyses of adverse events

Type of AE	MedDRA levels	Main period	LTE
All TEAE	Overview ^a Primary SOC, HGLT, HLT and PT	✓	✓
	Primary SOC and PT	✓	
	PT	✓	\checkmark
		✓	
TEAE related to IMP as per Investigator's judgment	Primary SOC and PT	✓	✓
TEAE by maximal intensity	Primary SOC and PT	✓	✓
TEAE Grade 3 or higher	Primary SOC and PT	✓	
Treatment emergent SAE	Primary SOC and PT	✓	✓
Treatment emergent SAE related to IMP as per Investigator's judgment	Primary SOC and PT	✓	✓
TEAE leading to permanent discontinuation of intervention	Primary SOC and PT	✓	✓
Bleeding event by grade ^b	Primary SOC and PT	✓	✓
Bleeding events (Intensity Grade 2 or higher) ^b	Primary SOC and PT	✓	✓
Related bleeding events (Intensity Grade 2 or higher) ^b	Primary SOC and PT	✓	✓

28-Nov-2022	
Version number:	1

Type of AE	MedDRA levels	Main period	LTE
Infection (Intensity Grade 2 or higher) ^C	Primary SOC and PT	✓	✓
Related infection (Intensity Grade 2 or higher) $^{\it c}$	Primary SOC and PT	✓	✓
TEAE by age group (<65, >=65 years)	Primary SOC and PT	\checkmark	
TEAE by gender	Primary SOC and PT	✓	
TEAE by concomitant ITP medications (No concomitant ITP medication, CS alone, TPO-RA alone, CS + TPO-RA)	Primary SOC and PT	✓	

a Will include the following AE categories: any AEs, any serious AEs, any AEs leading to death, any AEs leading to permanent intervention discontinuation

Analysis of deaths

Death will be listed.

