4.7.3 Additional safety assessments

4.7.3.1 Laboratory variables, vital signs, and electrocardiograms

The following laboratory variables, vital signs, and electrocardiogram (ECG) variables will be analyzed. They will be converted into International System of Units (SI) unless otherwise specified.

• Hematology:

- Red blood cells (RBC) and platelets: RBC, Hemoglobin, Hematocrit, Mean Cell Volume (MCV)*, Mean Corpuscular Hemoglobin (MCH)*, Mean Corpuscular Hgb Concentration (MCHC)*, Mean Platelet Volume (MPV)*, Red cell distribution width (RDW)*, Reticulocyte
- White blood cell (WBC) count with differential: WBC, Neutrophils, Lymphocytes, Monocytes, Eosinophils, Basophils
- Coagulation: prothrombin time/International Normalized Ratio (INR) and activated partial thromboplastin time (aPTT)
- Serum chemistry:
 - Metabolism: Glucose, Creatinine phosphokinase (CPK)
 - Electrolytes: Sodium, Chloride, Calcium, Phosphorus, Potassium
 - Renal function: Creatinine, Blood Urea Nitrogen (BUN)
 - Liver function: Aspartate aminotransferase (AST), Alanine aminotransferase (ALT), Total bilirubin, Direct bilirubin, Indirect bilirubin, Alkaline phosphatase (ALP), Albumin, Total Protein

b Bleeding events is identified by narrow search of SMQ = Haemorrhages

c Infection identified by primary SOC = "Infections and infestations"

- Thrombopoietin (TPO) levels
- Urinalysis*: Specific gravity, pH, glucose, protein, blood, ketones, bilirubin, urobilinogen, nitrite, leukocyte esterase
- Vital signs: blood pressures (BP), pulse, temperature* and respiratory rate* and body weight, height*
- ECG variables: pulse rate*, QT interval*, PR interval, RR interval*, QRS duration, QTcF interval and overall ECG assessments (normal, abnormal not clinically significant and abnormal clinically significant)
- Immunoglobulins: Immunoglobulin G, Immunoglobulin M, Immunoglobulin E (IgE), Immunoglobulin G Subclass 1, Immunoglobulin G Subclass 4
- Hemolysis Panel: Direct Coombs (Anti-Human Globulin), Haptoglobin

For descriptive summary, data below the lower limit of quantitation/detection limit (LLOQ) will be replaced by half of the LLOQ, data above the upper limit of quantification will be replaced by ULOQ value.

Quantitative analyses

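### Part B: Protocol 11.3 can keep non-serious bleeds typical for the patient off the AE page, so the Grade 2 or higher bleeding proportion, taken only from recorded TEAEs, may under-count

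*Protocol*

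**What the plan says.** Protocol 11.3 sets the recording rule: "Unexpected progression, signs, or symptoms of the disease under study (ITP) are not AEs and are not to be recorded on the AE page". Events that are serious, or inconsistent with the patient's typical course, are excepted. The next sentence covers worsening of ITP and says that "other disease-related symptoms should be recorded as an AE only if the event meets the definition of an SAE", again with atypical events as the alternative. The paragraph before it also sets aside expected variation in ITP activity. Bleeding is not named as an exemption there, nor in the visible list of adverse events of special interest (Protocol 11.9).

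For Part B, Protocol 3.4.1 and the synopsis safety endpoints say: "Bleeding TEAEs will be tabulated and a proportion of patients with a Grade 2 or higher bleeding event will be provided". The Part B SAP (4.7.2) carries this as a line in the TEAE overview and as rows of Table 5. Footnote b to that table gives the source: "Bleeding events is identified by narrow search of SMQ = Haemorrhages". The same section defines TEAEs as a subset of AEs.

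Bleeding is also measured outside the AE page. Change from baseline in IBLS is a Part B secondary endpoint (Protocol 10.3.2; Part B SAP 4.4.1), with by-visit and mean-score summaries (4.8.3). ITP-PAQ items 1, 3 and 4 ask about bruising or petechiae, mouth blood blisters and bleeding episodes over four weeks (Part B SAP Appendix 7).

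**The concern.** Protocol 1.1 describes a predisposition to bleeding as a consequence of ITP, so a rule about ITP symptoms reaches bleeding. If a site follows 11.3, a bleed that is non-serious and usual for that patient is not entered as an AE. It then has no CTCAE grade and no causality assessment, and it cannot appear in the Grade 2 or higher proportion or in the related-bleeding rows of Table 5.

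A reader will naturally take the proportion as the incidence of Grade 2 or higher bleeding on treatment. What it measures is the incidence of such bleeding that a site judged serious or atypical, plus whatever else the site chose to record. That judgement may differ between sites, and the wording does not help. The first sentence exempts signs described as *unexpected*, yet the same section requires events that do not fit the typical course to be recorded.

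**Working it through.** The documents state no bleeding rate and no planning figure for this endpoint, so there is nothing to reproduce. The check is of the text, followed by what arithmetic the documents allow.

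**1. The chain.**
- Recording (Protocol 11.3): an ITP symptom is entered as an AE only if it is serious or atypical.
- Definition (Part B SAP 4.7.2): a TEAE must first be an AE.
- Identification (Table 5, footnote b): bleeding is found by a narrow query on coded AE terms. No other source is named.
- Result: a non-serious, typical Grade 2 bleed kept off the AE page cannot enter the numerator. The rule removes events and adds none, so its own effect is downward.

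**2. Effect per patient.** With about 23 patients (Protocol 4.7), each patient whose Grade 2 or higher bleeds are all unrecorded lowers the proportion by 1/23 = 4.3 points. A patient with at least one such bleed recorded is still counted.

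**3. Illustration with assumed counts.** Suppose 4 of 23 patients truly have such a bleed. Exact 95% limits are the Beta quantiles B(0.025; x, n−x+1) and B(0.975; x+1, n−x), with the lower limit set to 0 when x = 0.

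| Patients with a recorded bleed | Proportion | Exact 95% CI |
|---|---|---|
| 4 (all) | 17.4% | 5.0% to 38.8% |
| 2 (half) | 8.7% | 1.1% to 28.0% |
| 0 (none) | 0% | 0% to 14.8% |

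Neither the 4 nor the recorded share comes from the documents.

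**4. Can the planned IBLS outputs stand in?** Not at patient level.
- *By-visit frequencies.* Six on-treatment post-baseline clinic visits are scheduled (Weeks 5, 9, 13, 17, 21 and 25; Protocol Appendix 4). Suppose one patient of 23 has a score of 2 at each visit. The share ever affected is 1/23 = 4.3% if it is always the same patient and 6/23 = 26.1% if it is six different ones. The by-visit table looks the same.
- *Mean score.* One item moving from 0 to 2 at one visit adds 2/11 = 0.18 to that visit's score (2/10 = 0.20 with ten items). Over six visits this is 0.18/6 = 0.030 to 0.20/6 = 0.033 on a 0 to 2 scale.
- *Coverage.* The history items recall one week (Part B SAP Appendix 5) and clinic visits are 28 days apart: 7/28 = 25% of treatment time. This is a floor, because the scale is also listed for early-withdrawal and unscheduled visits.

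**5. The ITP-PAQ.** Its recall period is four weeks and quality-of-life questionnaires are scheduled at the four-weekly clinic visits, so coverage in time is wider. However, the items ask how often something occurred and do not grade it, and the SAP plans only scale scores (4.8.3).

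**The case against.** The strongest reply is that the plan measures what it defines: Protocol 3.4.1 speaks of bleeding TEAEs and the SAP tabulates bleeding TEAEs. Other text presupposes that bleeding is recorded: Table 5 plans bleeding by grade, the Part A SAP schedules refer to following up bleeding adverse events, and Protocol 4.6.2 mentions AEs related to the disease. The first part stands, and as a count of recorded AEs the figure is valid. The second does not settle the matter, because all of these passages are consistent with only serious or atypical bleeds being recorded, and none overrides 11.3.

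It is also fair that the opening sentence of 11.3 exempts *unexpected* signs, so the loss of typical bleeds rests mainly on the sentence that follows. Sites may have recorded typical bleeds anyway. The serious category includes important medical events, so the affected class may be narrow. IBLS change is a named secondary endpoint and the ITP-PAQ adds patient-reported bleeding. All this limits the size. An exemption could sit in schedule footnotes or CRF guidance not visible here.

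Two stronger readings are tempting. A reader might infer that the effect on bleeding was unintended. The amendment 13 log explains that platelet count varies ("As such it is expected to fluctuate and is captured in the efficacy assessments"), and the amendment 14 log has "Updated to reflect decision to summarize all bleeding events". But the first does not show the superseded wording and the second concerns what to summarize, not what sites record. A reader might also infer that a key endpoint is compromised, because 3.4.1 is headed as primary safety. Part B SAP Table 2 does not list the proportion, the safety analyses are descriptive, and no visible decision rule uses it.

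**Conclusion.** The concern holds in a limited form. Followed as written, 11.3 allows non-serious Grade 2 bleeds that fit the patient's typical course to be left out of Part B's bleeding proportion. The effect of this rule is downward, at 4.3 points for each patient wholly missed, and its total cannot be determined. No visible planned Part B output gives the proportion of patients with any marked bleeding, so the report would contain no patient-level cross-check.

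This assumes that sites applied 11.3 to bleeding and that no exemption exists in text not shown. If one does, citing it closes the point, apart from the conflict between unexpected and atypical events, which needs reconciling in any case.

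A reader might extend the conclusion to Part A, since 11.3 is not confined to Part B. The documents do not establish that. The text of 11.3 in force before protocol amendment 13 is not shown, 47 of about 60 Part A patients were enrolled by 05 May 2020 (Protocol 1.2), and Part A uses a broad query with medical determination (Part A SAP 5.5.4), so its total error need not run one way.

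**What to change.** **1. Part B SAP addendum and report.** Label the figure *bleeding recorded as AEs; may under-count because of Section 11.3*. Add one descriptive table from existing IBLS data, marked post hoc: the proportion of patients with any site worsening from baseline to that site's maximum score at any post-baseline visit, with the number already at maximum at baseline. The maximum is 2, except for subconjunctival haemorrhage, where it is 1. State that IBLS scores are not CTCAE grades, that scheduled one-week recall covers about 25% of treatment time, and that the table supplements the TEAE figure without correcting it. Refer to the ITP-PAQ bleeding items as further context.

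**2. Remaining LTE follow-up.** Reconcile 11.3 with the bleeding endpoint, and resolve the conflict between exempting unexpected signs and requiring atypical events to be recorded. If recording changes as a result, report LTE bleeding before and after the change separately.

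**Cost.** The first part is one label and one table, necessarily post hoc because preliminary results of both parts are known (Protocol 2.2), and it describes the bleeding figure less favourably. The second needs an amendment with ethics approval and, if substantial, health-authority approval (Protocol 13.4). A change in recording could make LTE bleeding less comparable with the main period. Amending 11.3 cannot repair main-period AE data: all Part B patients had finished 24 weeks when the SAP was approved.
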